3.2 SCHEDULE OF ACTIVITIES

Below is a table detailing the key activities in intervention and control communities, from baseline through the end of the study.

Table 1. Detailed Overview of Activities by Control and Intervention Sites

	Planning	Baseline	3-month	6-month	9-month	12-month	15-month	
INTERVENTION AND CONTROL	 							
Pilot survey (phone or in-person) and qualitative interviews	Х							
Baseline BMU Census/ Registry verification & updating	Х	Х						
Eligibility screening and informed consent		Х						
Baseline survey		Х						
Social network mapping and randomization		Х						
Follow up survey – (includes HIVST self-report)			Х					
Qualitative in-depth interviews and focus group discussions (HIVST and network support)			x	х				
Linkage to ART or PrEP				х				
VL measurement and adherence for those initiating ART				х				
Urine tenofovir levels measurement and adherence for those initiating PrEP				х				
Qualitative in-depth interviews (Linkage and retention)				х				
INTERVENTION								
Enhanced training (HIV basics, HIVST, PrEP, and ART)		х	x	x				
HIVST for distribution via network-central promoters		Х	Х					
Voucher for cash redemption 500 KSH (at clinic linkage)		Х	Х					
Enhanced promoter support/training		Х	Х	х				
Retention support via SMS/phone			Х	х				
CONTROL	· ·							
Basic training (HIV basics and facility access/info)		х						
Voucher for HIV test or HIVST redemption at facility		Х	х					
Standard of care for ART or PrEP		Х	Х	х				

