HIV-negative participants who screen as eligible and enroll in PrEP, and who give their informed consent will provide, in clinic, the urine specimen for measurement of PrEP adherence. The device used for testing is the PUMA Point of Care urine monitoring assay for TFV- Alere. It is not invasive and is merely a testing tool to determine if the patient is taking tenofovir or not at time of a clinic or study visit. Tenofovir is a mainstay of both HIV treatment and prevention and adherence to tenofovir-containing regimens is paramount for efficacy. Given that the effectiveness of PrEP is tightly linked to adherence, a real-time method of measuring tenofovir adherence is desirable. This immunoassay will test for tenofovir detection at a study visit using urine samples. This test is exempt because it is non -invasive (tests tenofovir detection in urine, which is collected noninvasively) and is diagnostic. The study will be working with facilities implementing PrEP (per MOH guidelines) and will work with providers to integrate real-time PrEP adherence monitoring for study participants only. Study participants will be provided PrEP per the MOH guidelines and will come in for their routine visits. At the 6-month -month visit, we will train MOH providers to include the PUMA assay for monitoring adherence. The providers will also administer a brief survey to assess participant adherence to PrEP at the 3-month **and** 6-month visits. As part of boosting

PrEP knowledge, we will use an informational sheet on PrEP available in the local languages, to provide standardized information to participants on PrEP's purpose to prevent HIV acquisition.

Performing and Interpreting Urine Tenofovir Adherence Assay

1. Present patient with a cup and ask them to please provide a urine sample. Of note, there is no need to clean the urethra prior to urine collection. The patient can just urinate into the cup (about 5-10mL). Please ask them to urinate into the pit latrine if they have excess urine after filling the cup to the line.

2. Please ask the patient to screw the lid on to the urine cup after collection and bring it back out to the provider.

3. The provider (using gloves) should use the dropper provided with the urine test to drip 3-4 drops of urine from the urine cup into the divet of the urine test strip (indicated by blue arrow on below picture).

4. After putting the urine drops on the the urine strip test, please lay it on a paper towel and let it develop for 2-3 minutes

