8.10 TEXT MESSAGE REMINDERS

To the extent that men on PrEP and ART are willing, optional cell phone appointment reminders and text messages motivating adherence will be sent to them (including promoters). These messages will be motivational, will not include any identifying information and will include generic texts such as "maintain your good health", to cater for status-neutral language that can work for both HIV positive individuals taking ARVs, as well as HIV-negative individuals on PrEP who may need adherence support.

Sample language for these text messages are included in the table below. These sample texts will be further refined with the input of the community and our peer leaders to ensure that they are locally and culturally salient and relevant. We will ensure these messages are status-neutral and non-stigmatizing to ensure they are relevant and do not compromise patient confidentiality.

Table 4. Sample Text Messages to Facilitate Adherence

It is important to maintain your health.
Please prioritize your health and well-being to stay strong.
Please remember your appointment.
If you need support to make your appointments, please reach out to your provider.
Your provider can help keep you healthy, please reach out if you need help.
Be healthy, have a healthy happy family!
Be healthy, be productive!

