1.3.3 ANALYSIS OF ADDITIONAL ENDPOINT(S)

Primary Outcome: the primary outcome measure will be linkage to care or prevention within 3 months of the Aim 1 intervention start. Linkage will be defined for HIV-positive participants as a documented confirmatory HIV test result, and a documented HIV clinic visit following referral. Linkage will be defined for HIV-negative participants as documented evidence of evaluation for PrEP (following standard of care procedures) extracted from medical records.

Secondary outcome: The secondary outcomes will be confirmatory HIV testing uptake 3 – 6 months after intervention start and the initiation of ART, or PrEP (among those screened as eligible), within 3 months of the confirmatory test or eligibility screening. HIV testing uptake will be measured via documented testing records in clinic records and ART start will be measured via documented prescription for ARV medications, and for PrEP start, via oral PrEP prescription.

Third outcome: The third primary outcome is a composite measure meant to capture "success" in HIV prevention and/or treatment behaviors. The measure will be defined as either adequate levels of tenofovir, indicating PrEP adherence (defined as TFV levels of >= 1500 ng/mL in urine indicating adequate adherence vs. < 1500 ng/ml) among HIV seronegative individuals who screened eligible for PrEP or the proportion of HIV-positive participants with viral suppression (defined as HIV RNA <400 c/mL using the Abbott realTime HIV-1 platform and assay, with a detectable threshold of 40 cells per microliter at 6 months. PrEP adherence will be measured at 6 months after initiation using our novel technology of point-of-care rapid testing to assess TFV adherence in urine (developed by Co-I [name] in collaboration with Alere Rapid Diagnostics[™]). For both components of the measure, we will define missing values as failure (i.e. inadequate adherence or unsuppressed).

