In networks randomized to the intervention, promoters will then be given multiple self-tests labeled with a unique network specific number, and they will be encouraged to offer self-tests to men in their close social networks and to motivate them to use the self-tests privately or with their support. During training, each promoter will be asked to demonstrate self-test use in order to confirm correct understanding of this process before they are asked to offer the self-tests to their peers. Training will also cover best practices on self-test distribution and role-playing of multiple potential distribution and promotion scenarios (we will build upon materials we developed in other HIVST studies). By the end of the training, promoters will be capable of explaining self-test usage to others and have

guidance on which individuals they offer self-tests to. Promoters will be encouraged to offer self-tests to their close social network members only, and not others in their community.

SMS messages (not individualized) with status neutral messaging will be sent out to participants in the intervention arm to promote ART/PrEP retention.

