### 15) Timing of outcome assessments:

Research staff will collect data from all study participants in both arms at approximately 0 months/baseline, 3 months, 6 months, and 12 months. All assessments will have a window of +/- 1 month. Outcome assessments collected via clinical chart abstraction (HIV confirmatory testing and results, PreP screening and uptake, and ART screening and regimen, clinic attendance), survey (self-reported testing), and via specimen collection and analysis (HIV viral load testing and PreP adherence) will be assessed within one month of each participant's 6 or 12 month outcome window, through a study-scheduled visit.

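### Attendance support is listed for the intervention arm only, Aim 3 scores an unmeasured man as a failure, and no planned between-arm analysis separates attendance from suppression or PrEP adherence

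*Protocol*

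**What the plan says.** **Who gets attendance support.** Table 1 in protocol 3.2 has a row "Retention support via SMS/phone" in the 3- and 6-month columns under the intervention heading, with no counterpart under control. SAP 10 says "SMS messages (not individualized) with status neutral messaging will be sent out to participants in the intervention arm to promote ART/PrEP retention". Protocol 8.9 offers promoters in the intervention arm up to four further sessions, in which they are urged to get men who started ART or PrEP back to clinic. Protocol 8.10 is the only section that describes appointment reminders. It says that "optional cell phone appointment reminders and text messages motivating adherence will be sent to them", meaning willing men on PrEP or ART, and it names no arm.

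**How the outcome is obtained.** Under protocol 8.7, viral load comes from blood drawn at a 6-month study visit. Urine is given in clinic, with an assay used to "determine if the patient is taking tenofovir or not at time of a clinic or study visit". SAP 15 places these assessments within one month of the participant's "outcome window, through a study-scheduled visit".

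**How missing results are scored.** Protocol 1.3.3 states: "For both components of the measure, we will define missing values as failure". SAP 26 and 28 apply the same rule in the intention-to-treat analysis.

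**What else is planned.** SAP 27f enters sensitivity analyses as not applicable, SAP 20c excludes complete-case analysis, and SAP 29 requires no additional analyses. The per-protocol set in SAP 20b contains intervention-arm men only.

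**The concern.** A man who misses the 6-month visit has no specimen and is scored unsuppressed or non-adherent, whatever his true state. If one arm receives more support to attend, its success proportion rises through attendance even when men in both arms are equally suppressed and adherent.

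The SAP's Aim 3 hypothesis concerns rates of suppression and PrEP adherence, and retention has its own outcome and test. A positive Aim 3 result could be reported as better virological control or better drug-taking when some of it is better attendance at the visit where these are measured. No planned between-arm analysis would show which. The per-protocol set cannot help, because it has no control group.

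**Working it through.** **1. Reproduce the plan's Aim 3 power.** Inputs from protocol 1.2 (Aim 3): 168 men on PrEP plus 72 on ART = 240; control success 70%; intervention success 89%; design effect 1.7. Allocation is 1:1 (protocol 6.5) and the test is two-sided at 5% (SAP 16).

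- Men per arm: 240 / 2 = 120. Effective number: 120 / 1.7 = 70.6.
- Pooled proportion: (0.70 + 0.89) / 2 = 0.795. Null standard error: √(2 × 0.795 × 0.205 / 70.6) = 0.0680. Alternative standard error: √((0.70 × 0.30 + 0.89 × 0.11) / 70.6) = 0.0660.
- Power = Φ((0.19 − 1.96 × 0.0680) / 0.0660) = 80.5%. The plan states at least 80%, so this model matches the plan.

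**2. Write the outcome as the rule defines it.** With missing scored as failure:

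observed success = proportion attending × success among attenders.

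**3. Attendance-only difference.** The documents give no expected attendance at the 6-month visit, so the following are assumptions. Control attendance is 80% and success among control attenders is 87.5%, which returns the plan's control rate: 0.80 × 0.875 = 0.70. Intervention attendance is 85%, 90% or 95%. Men who would have attended anyway succeed at 87.5% in both arms. Let *e* be the success rate among the extra attenders.

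Observed intervention success = 0.70 + (extra attendance × *e*). The rejection probability uses the test in step 1 with 70.6 effective men per arm.

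| Intervention attendance | *e* = 87.5%: observed | Difference (points) | P(significant) | *e* = 50%: observed | Difference (points) | P(significant) |
|---|---|---|---|---|---|---|
| 80% | 70.0% | 0 | 5% | 70.0% | 0 | 5% |
| 85% | 74.4% | 4.4 | 9% | 72.5% | 2.5 | 6% |
| 90% | 78.8% | 8.8 | 22% | 75.0% | 5.0 | 10% |
| 95% | 83.1% | 13.1 | 45% | 77.5% | 7.5 | 17% |

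Example: 0.70 + 0.10 × 0.875 = 0.7875 and 0.70 + 0.10 × 0.50 = 0.75. The planned difference is 19 points.

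**4. A reference point from the plan.** Protocol 1.2 powers retention at 81% against 96%. If visit attendance followed those figures (again an assumption), equal success among attenders of 0.70 / 0.81 = 86.4% gives 70.0% against 0.96 × 0.864 = 83.0%. That is 13.0 points, or 13.0 / 19 = 68% of the planned effect, significant 44% of the time.

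**5. What success among men measured would show.** With *e* = 87.5% it is 87.5% in both arms, which exposes the attendance effect. With *e* = 50% and 90% attendance it is 0.75 / 0.90 = 83.3% in the intervention arm against 87.5% in control, because the extra attenders dilute it. It helps interpretation but is not an unbiased comparison.

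**The case against.** The strongest reply is that combining attendance with biology is legitimate and partly intended. Protocol 1.1 hypothesises that more men will be both retained and adherent, protocol 1.3.3 calls the outcome a composite of success, and retention support is a listed intervention component. This stands: missing as failure is a defensible primary rule. What it does not supply is any way to interpret the result as suppression or adherence.

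A reader might infer that appointment reminders certainly go to one arm only. The documents do not establish that. Protocol 8.10 names no arm, Table 1 speaks of retention support, and the SAP's messages are not individualised, which fits poorly with a dated visit reminder. If 8.10 governs, the text-message imbalance disappears, but the promoter encouragement in 8.9 remains intervention-only.

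A reader might also infer that a text shortly before the visit raises the urine reading. Nothing times any message to the test, so this is conjecture.

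Nor is the 6-month visit purely a research measurement. Ministry of Health providers run the urine assay alongside routine PrEP care, and PrEP users are 168 of the 240 projected men. Only the viral-load draw is clearly study-run.

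Arm-neutral measures exist: 500 KSh for the 6-month visit in both arms (protocol 8.11), tracing through trusted friends (9.2), and loss to follow-up tabulated by arm (SAP 24). They may narrow an attendance gap but do not separate attendance from success.

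Finally, the size depends on assumed attendance gains and on how the extra attenders fare.

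**Conclusion.** The concern holds in this form: attendance-directed support is listed for the intervention arm only, Aim 3 needs a specimen from a visit, and non-attendance is failure. The primary contrast is therefore of men seen and successful, and the planned analyses cannot say how much of a difference is attendance.

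Under the stated assumptions, attendance gains of 5 to 15 points alone produce 2.5 to 13.1 points against a planned 19, with a significant result 6% to 45% of the time instead of 5%. These figures illustrate the mechanism. They do not predict the trial's error rate, since the documents give no attendance figures and a real effect on drug-taking may coexist.

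It does not follow that the missing-as-failure rule is wrong, or that every attendance-driven gain is spurious. Bringing men back to care is part of what the intervention is meant to do.

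**What to change.** - **SAP 26 and protocol 1.3.3:** keep missing as failure as primary, and describe it as a combined retention-and-success outcome.
- **SAP 27f and 28:** replace the not-applicable entry with a prespecified report by arm of (a) the proportion measured, for viral load and urine separately; (b) success among men measured; and (c) a multiple-imputation or bounds analysis for men not measured. Revise SAP 20c to permit (b) as supportive.
- **Protocol Table 1, protocol 8.10 and SAP 10:** reconcile which arm or arms receive appointment reminders.
- **Protocol 8.7, viral-load draw:** use the same scheduling contact and tracing attempts in both arms. Extending this to PrEP men is a trade-off, because their specimen visit is largely routine care and a reminder would add attendance support to the control condition.

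The cost is a little more analysis, some wording, and equal contact effort for one study-run visit. Success among men measured conditions on a post-randomisation event, so it should be labelled supportive only. If the visits are already complete, the reporting changes can still be made.

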4 INTRODUCTION

4.1 STUDY RATIONALE

Ending the AIDS epidemic in sub-Saharan Africa (SSA) will require further engagement of men in HIV testing, prevention, and treatment, a challenging task given that nearly 50% of HIV-positive men in many countries are unaware of their HIV status and men have lower uptake of HIV treatment and pre-exposure prophylaxis (PrEP).^{1,2} In SSA, highly mobile men such as those working in fishing communities alongside Lake Victoria have low uptake of HIV testing and low rates of linkage to HIV treatment and PrEP, despite increasing availability of these services. As a result, HIV transmission risks remain high in these communities. Two recent innovations – HIV self-testing (HIVST) and social network-based interventions – hold promise for overcoming barriers to HIV testing and linkage to services for HIV-positive and HIV-negative men. This study seeks to determine if an HIV status-neutral, social network-based approach can promote HIV testing, linkage to care and prevention, and better health outcomes in men.

We focus on a highly mobile population of men: fishermen in communities on Kenya's Lake Victoria shoreline, where HIV incidence (2.4-9.3 per 100 PY)^{3,4} and prevalence (24-26%)⁵⁻⁷ remain high despite progress elsewhere, ^{3,5,8-10} and where treatment uptake is only 53-61%.^{5,6} Our prior work showed that mobility of fisher folk and a transactional sex economy contribute to their exceptionally high HIV risks.¹¹⁻¹⁵ Low rates of testing and care engagement among fishermen are influenced by the mobility inherent to their livelihoods, stigma in beach communities, and gender norms.¹⁶⁻¹⁸ new strategies specifically targeted to reach highly mobile men are urgently needed to increase men's testing uptake and linkage to ART and PrEP

This study will leverage new technologies and insights from behavioral economics and social network research to test low-cost, scalable interventions to close gaps in the prevention and care cascade. To increase uptake of HIV testing and existing prevention and treatment services, we will test a strategy that recruits and trains highly-connected, network-central men to distribute HIV self-tests and provide linkage support to men in their close social networks. Men due to its convenience and privacy prefer HIVST.^{19,20} Policies are evolving rapidly, with WHO recommending HIVST scale-up and the Gates Foundation subsidizing self-test prices. Building on our studies of secondary distribution of self-tests by women,^{21,22} financial incentives,²³⁻²⁵ and adherence metrics²⁶⁻²⁹ to objectively assess outcomes, as well as other research demonstrating the importance of social networks for influencing norms and behaviors,³⁰⁻³⁸ we will evaluate an innovative social-network based approach to promoting HIV prevention and treatment behaviors among men. Network-central promoters – who are well positioned to disseminate information and influence behaviors – will distribute HIV self-tests, transport vouchers for referral services, and information on ART and PrEP, to men in their networks. Specifically, we will conduct a cluster-randomized trial of social network-based self-test distribution and linkage intervention among 80 close social networks of men in Kenya.

4.2 BACKGROUND

Men's engagement in HIV prevention and care remains suboptimal, especially in high priority settings in sub-Saharan Africa (SSA). Ending the AIDS epidemic requires interventions that can achieve higher uptake of HIV testing, particularly among the ~50% of HIV-positive men in many countries who are unaware of their HIV status.^{1,2} It also requires interventions to successfully link HIV-positive individuals to existing services for antiretroviral therapy (ART) and high-risk HIV-negative individuals to prevention including HIV pre-exposure prophylaxis (PrEP). A focus on men is warranted because, relative to women, men test for HIV at lower rates, ³⁹ are less likely to engage in HIV treatment and PrEP programs,^{1,2} have higher attrition from treatment programs,⁴⁰⁻⁴⁵ and have higher rates of viral failure on ART.^{5,46-49} This results in men's lower life expectancy on ART^{50,51} as well as their continued onward transmission of HIV to women.⁵² This proposed study addresses the high priority research needs identified in PA-19-042, Engaging Men in HIV Testing, Prevention, and Care.

We know that men's barriers to HIV prevention and care engagement are both structural (e.g. laborrelated mobility) and cultural (e.g. gender norms). We and others have identified structural and cultural barriers, including men's labor-related mobility, and gender norms that valorize risk-taking and discourage health-seeking behavior, that have contributed to men's lower participation in HIV testing relative to women.^{16,53} While men's enactment of masculinity (i.e. behavior that fulfills male gender role expectations) often results in personal advantage, these same constructs and associated behaviors also serve to configure vulnerabilities for men in terms of HIV acquisition, HIV care engagement, and HIVrelated mortality.^{41,43,53-61}

This study focuses on a particularly high-priority population of men residing in communities along Lake Victoria. HIV incidence remains high among fisher folk despite progress against the spread of HIV elsewhere in the region.^{3,5,8-10} Recent studies estimate HIV prevalence is 24-26%⁵⁻⁷ and incidence is 2.4-9.3 per 100 PY,^{3,4} yet treatment coverage is only 53-61%.^{5,6} [name] research has revealed that the mobility of fisher folk coupled with a "sex-for-fish" economy (locally called "jaboya", in which fishermen give female traders access to fish in exchange for sex), contributes to their exceptionally high risks.¹¹⁻¹⁵ Our team and others have found low rates of HIV testing and care engagement among fishermen are influenced by structural factors – fishermen find it difficult to access services at fixed-location clinics and typical clinic hours because of their mobility – and cultural factors such as HIV-related stigma and gender norms counter to men's health-seeking behaviors, e.g. HIV testing "by proxy" (i.e. inferring their HIV status from their female partners' test results).^{16-18,62} In this setting of high risks,^{6,63} where 10% of adults have undiagnosed HIV and 60% of HIV-positive people need ART,⁵ strategies are urgently needed to increase men's testing uptake and linkage to ART and PrEP Moreover, HIV status-neutral approaches are needed to counter HIV-related stigma among fishermen.

The research to date reveals several scientific and implementation knowledge gaps: What are the best approaches to engaging highly mobile, high-risk men to increase their uptake of HIV testing and linkage to ART and PrEP? Given that conventional testing and care delivery approaches have not been successful to date, what new strategies are needed to address men's well-known barriers, including work-related mobility?

HIV self-testing (HIVST) presents an excellent opportunity to bridge these gaps. A growing literature shows that HIVST is safe and can overcome barriers to clinic-based, counselor-administered testing. With HIVST, individuals collect their own oral fluid sample and perform a simple, rapid antibody test in the absence of a provider. Studies show high acceptability and demand for HIVST across many populations and settings, as it offers convenience, privacy, and accuracy among lay users.^{19,64-73} Interest is typically highest among high-risk groups and those who have never tested.⁷⁰

Providing multiple self-tests to men and encouraging them to distribute tests to men in their social networks (i.e. 'secondary distribution') is a promising but untested strategy to increase men's testing. Secondary distribution of self-tests within social networks may be a low-cost, efficient way to increase testing coverage. We and others have shown that secondary distribution of self-tests by women to their male partners is an effective way to promote partner and couples testing; ^{21,22} such approaches are now being implemented in many countries.⁷⁴ However, this approach may not be feasible for all women and it does not sufficiently leverage the fact that men are highly influenced by their peers. To date no studies have assessed the impact of secondary distribution of self-tests in men's social networks – an important evidence gap regarding HIVST.

Countries in SSA are scaling-up HIVST to close the testing gap in priority populations – evidence is needed on delivery approaches that maximize testing coverage. A growing number of countries, including Kenya, are scaling-up HIVST after the WHO's December 2016 guidelines called for large-scale implementation of HIVST.⁷⁵⁻⁷⁷ The feasibility of HIVST interventions was further enhanced by the Gates Foundation's 2017 decision to subsidize oral fluid-based HIV tests, bringing their price down to \$2/test. What countries are actively seeking are optimal distribution strategies for self-tests, to ensure that testing is increased among high-risk individuals not reached by other HIV testing modalities.

Social network-based approaches show promise for generating positive social influence and accelerating health behavior change in men. The influence of social networks on health behaviors and outcomes is well established⁷⁸⁻⁸⁴ and it is known that social network characteristics can influence behavior through the circulation of ideas and social influence.⁸⁵ Network interventions are purposeful efforts to use networks to generate social influence, accelerate behavior change, and achieve positive health outcomes.⁸⁶⁻⁹¹ In SSA, prior research has shown the influence of social networks on HIV testing, ⁹²⁻⁹⁴ partner concurrency, ⁹⁵ and condom use.⁹⁶ Such an approach is further supported by research showing that behavioral and organizational change programs are most effective when implemented by members of the group undergoing the change, i.e., peers.^{97,98} We also now know that selecting influential nodes in a network (i.e. individuals who are highly connected) results in superior intervention effectiveness: selecting well-connected nodes, from a network perspective, are better than nodes chosen randomly, a finding demonstrated with simulations ^{99,100} and empirical examples.^{101,102} Thus, selecting highly socially connected men within social networks to act as 'promoters' may overcome long-standing barriers to HIV testing and uptake of additional health services.

To maximize the HIV prevention potential of HIVST, interventions are needed to promote linkage to care and prevention. As with strategies including home-based and community-based HIV testing, linkage rates following HIVST are often suboptimal without other interventions to motivate confirmatory testing and linkage to care and prevention. Given the absence of a counsellor during HIVST, it is arguably even more important to promote linkage interventions with HIVST. A recent WHO summary of the few HIVST studies conducted (usually without linkage interventions) reported that linkage after HIVST was 50-56% in general populations in SSA.⁷⁵ In its 2016 HIVST guidelines, WHO emphasized a need for evaluation of interventions to facilitate linkage to care and prevention. We will directly address this "Achilles heel" of HIVST with social network approaches and low-cost financial incentives, both intended to promote linkage to care.

PrEP has the potential to reduce HIV incidence in SSA, but there are many knowledge gaps concerning PrEP implementation, especially in men. Trials have proven the efficacy of PrEP,¹⁰³⁻¹⁰⁸ but varied protection levels have been attributed to low adherence: in trials in young women, adherence was too low to demonstrate effectiveness.^{104,106} PrEP non-use was influenced by partners and peers,^{109,110} and many women perceived themselves to be at low HIV risk. In a trial in discordant couples in which adherence was higher,¹⁰³ only 20% of those at high risk reported they were at risk.¹¹¹ while much has been learned about PrEP adherence among couples and young women, and current interventions (e.g. DREAMS) focus on these populations, much less is known about men's demand for PrEP Our team has implemented PrEP in high-risk populations in the SEARCH trial,^{112,113} and low enrollment (~18%¹¹⁴) supports a need for strategies to stimulate uptake and adherence in this group. Moreover, self-reported adherence has proven limited in PrEP and objective adherence metrics using drug levels measure adherence more accurately.¹¹⁵ This study will fill key knowledge gaps by testing novel strategies to promote PrEP uptake, as well as to measure PrEP adherence among men.

Behavioral economics theories provide a strong rationale for using small financial incentives to promote healthy behaviors such as linkage to care and prevention. Insights from psychology and economics point to various factors and decision-making biases, such as limited attention and present bias,¹¹⁶⁻¹²⁰ that make financial incentives valuable strategies for promoting healthy behaviors. Studies in low-income countries show that providing small financial incentives results in significant behavior change.¹²¹ Trials conducted by our team in eastern Africa and others have shown that providing small incentives can promote uptake of services such as vaccinations, HIV testing and male circumcision, ^{23,121,122} warranting testing whether incentives promote linkage to appropriate available health services (ART or PrEP) after HIVST. The cost-effectiveness of incentives as a demand creation intervention for HIV prevention has led several programs and countries to adopt them on a larger scale, demonstrating the potential for sustainability. For example, revised WHO Guidelines of VMMC include recommendations for providing small amounts of compensation to clients in order to offset time cost and lost wages. This study will use a rigorous design to assess whether incentives, embedded within a social network approach, can promote ART/PrEP linkage, uptake and adherence.

